## **Participant Contact Project Narrative**

## 1. Summary

The Infinitome Program from Omniscient has the ability to study abnormal brain networks or connectomes using resting state functional MRI (rs-fMRI). This technology, which visualizes brain networks in three dimensions, was originally developed to ensure neurosurgeons avoid inadvertently lesioning cognitively eloquent brain regions during surgical operations. The potential of Infinitome in identifying connectome dysfunction for neurodegenerative diseases such as Alzheimer's disease has yet to be explored. This diagnostic technique may play a critical role for identifying disease brain networks that may benefit from targeted interventions in clinical trials.

## 2. Study aims

To determine the feasibility of utilizing Infinitome Program for the evaluation of network dysfunction in Alzheimer's disease. We will report the rate of completion of rs-fMRI, rate of completed analysis of images using the program, and list the abnormal networks as identified by the program.

## 3. Background, Rationale, Significance

In 2009, the Human Connectome Project (HCP) commenced one of the most ambitious neuroscientific initiatives to map the brain . This project identified 379 functional areas of the brain and gained insight into how they are connected, and how they related to neurological illness. This data has provided neuroscientists for the first time in history the ability to view the brain not merely as a structural entity, but rather as an individualized network system.

Unfortunately, the HCP has had little impact on clinical care. The techniques necessary to produce connectomic maps were feasible in research settings, but not clinical ones. Much of the work depends on the ability to perform rs-fMRI imaging as well as diffusion tensor imaging, both techniques that are time-consuming and impractical for clinical practice . At the same time, structural brain MRIs are too often read as "normal," even though a patient may carry a chronic, life-changing diagnosis of Alzheimer's disease or Lewy body dementia. These observations suggest that structural MRIs lack precision for the detection of brain abnormalities in patients with neurodegenerative diseases.

The Infinitome Product developed by Omniscient was created to accelerate connectomic research and provide application of rs-fMRI findings to the clinical setting. The product is cloud-based, accessible via internet browser, and has the capability to analyze rs-fMRI data from a clinic-based image server (see attached Omniscient Overview pdf file). The program allows for personalized connectome mapping, which enables visualization of brain networks with great accuracy, regardless of brain lesions. Furthermore, the developers have used machine learning to measure connectivity between subregions and how they compare to normal controls. For instance, the default mode network (DMN) has been found to function abnormally in Alzheimer's disease . This technology has the capability of comparing the DMN in a suspected Alzheimer's patient with a cohort of controls from the HCP.

This feasibility study may provide helpful clinical information relating to the underlying disease process and guide our practice. Furthermore, this information will be helpful in guiding our decision about purchasing a subscription to Infinitome for future clinical research. In addition the results will add preliminary data for a future grant applications that will utilize the program to detect abnormalities in AD and guide individualized treatments.

## 4. Approach

## a. Study design

This is a prospective feasibility imaging study in patients with AD.

## b. Population

i. Inclusion/Exclusion Criteria

**Inclusion Criteria** 

- 1. Patients with a diagnosis of mild, moderate, or severe Alzheimer's disease
- 2. Age: 40 90 Years
- 3. Patients who are clinically indicated for an MRI

#### **Exclusion Criteria**

- 1. fMRI contraindicated (eg. Implantable device, pacemaker, metallic implants, etc.)
- 2. Subject unable to tolerate sitting for a one hour fMRI
- 3. Other concerns as determined by the investigator
  - ii. Sample Size

We plan to enroll 4 patients

- c. Data collection process
- 1. [name] will identify potential study patients via scheduled clinic (or video visits) and ask patient/caregiver if they would like information about a research study and potential study participation.
- 2. If patient/caregiver indicates they would like more information, [name], shares the info with the research staff, and let patient/caregiver to expect a call from the research staff
- 3. Research staff reaches out to the patient/caregiver with a phone call (phone script attached), and patient/caregiver is offered an informed consent form to read on their own time. If the patient/caregiver requests additional time, then the research staff schedules a phone appointment to answer any questions, and to complete the electronic consent via REDCap. This process will be conducted prior to the scheduled imaging visit.
- 4. After completion of the informed consent process and upon confirmation of eligibility (I/E criteria), subject will undergo added imaging (research sequences).
- 5. Once the scan is complete, the data will be de-identified and uploaded to the Omniscient Cloud server. Once processed by the Infinotome program, the results will be collected by the research team and stored in a secure server. This information will also be shared with the patient and family.

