## **Resting state fMRI**

- $3 \times 3 \times 3$ -mm voxels
- 128 volumes/run
- TE = 27 ms
- TR = 2.8 s
- field of view = 256 mm
- flip angle = 90°
- Run time about 8 min

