# e. Outcomes/endpoint and other variable definitions, and instruments used

Since this is a feasibility study, we are mainly evaluating the ability of the Infinitome program to detect connectome abnormalities in AD subjects.

- Rate of Completion of rs-fMRI % of subjects who completed the sequence of the fMRI protocol
- Rate of Completed Analysis % of subjects whose images were uploaded and analyzed by the Infinitome program
- Type of Abnormal Networks Identified All the abnormal networks as identified by the Infinotome program (categorical) such as default modal network..

Variable Name	Data Source	Purpose	Measurement Scale
	(patient survey, EMR, claims, registry)	(sample identification, description, grouping variable, study endpoint, predictor, covariate)	(binary, continuous)
Demographics (e.g., Age, Gender)	EMR	Description	Continuous, Binary
AD severity	EMR	Description	Categorical
MoCA (Montreal Cognitive Assessment)	EMR	Description	Continuous
fMRI – Program numbers and Post- processed Images	MRI and Infinitome program	Description/endpoint	Descriptive/Continuous

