## g. Statistical analysis plan

Demographics and baseline characteristics of study participants will be summarized using descriptive statistics (mean and standard deviation, median, and proportions, as appropriate).

We will report the proportion of successfully completed rs-fMRIs and completed Infinitome analyses. If all 4 rs-fMRIs are completed and at least 3 of 4 Infinitome analyses are completed, we will consider this feasibility study a success.

We will also explore and report if any and which networks are identified as abnormal by the Infinitome program. The Infinitome output provides pairwise dysfunction between structures/areas within each network. We will report the number of patients who have dysfunction in the DMN, overall, as well as the number of pairwise structures within the DMN are dysfunctional. We may report on several other networks, if abnormality is shown.

h. No inferential statistics will be conducted for this study. We do not anticipate being able to definitively report areas that have dysfunction in persons with Alzheimer's; however, this preliminary data will be very important for future larger studies. Power analysis or statement of precision

If all 4 rs-fMRIs are completed and at least 3 of 4 Infinitome analyses are completed, we will consider this feasibility study a success. With a sample size of 4, we will be able to estimate a success rate of 75% to within a 95% confidence interval of +/- 21.7% assuming a true success rate of 75%.

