## i. Strengths and limitations

Strengths of this application include the fact that we are testing a novel program that leverages HCP data to determine dysfunctional connectomes in AD. This work has never been done before with this software and could lead to the design of clinical trials for targeted treatments to dysfunctional networks.

Limitations of this study include the low number of subjects, but we are merely performing a feasibility study to justify standard use of the Infinitome program in clinical research

5. Setting/Environment/Organizational feasibility

The study will be conducted at HealthPartners Neuroscience Center, specifically the Center for Memory and Aging. This location is appropriate in that it is an established multidisciplinary clinic developed specifically for evaluating patients with dementia. It is adequately staffed and equipped to serve this population.

As this study involves in-person visits, here is a description of how the visits will be conducted

- Visit would be added onto existing clinical care order. The only in-person visit is an increase in the amount of time for an already ordered clinical care MRI. NSC procedures would be followed. No additional scripting will be added.
- We plan to do the consent virtually. No in-person contact for consent process.
- 6. Risks and Benefits

The risk is overall minimal for patients. Structural MRI is a routine diagnostic procedure at HealthPartners, and the resting state portion merely requires an additional 8-15 minutes of scan time. The patient may experience claustrophobia with the narrow imaging space.

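### Does a one-hour tolerance screen undermine the completion rate for a resting-state sequence of about 8 minutes?

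*Combined protocol and SAP*

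**What the plan says.** Section 4.b excludes a "Subject unable to tolerate sitting for a one hour fMRI". Three other places bear on scan length:

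- Section 4.d, Resting state fMRI: "Run time about 8 min", with 128 volumes per run and a TR of 2.8 s.
- Section 6: "the resting state portion merely requires an additional 8-15 minutes of scan time".
- Section 5: "The only in-person visit is an increase in the amount of time for an already ordered clinical care MRI".

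Section 4.d also specifies a diffusion sequence with one b0 image and 30 to 60 directions, acquired before any contrast images. It gives no duration for that sequence. No section states the length of the clinical MRI or of the whole session.

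The first outcome in Section 4.e is the percentage "of subjects who completed the sequence of the fMRI protocol". Under Section 4.c, eligibility is confirmed before the research sequences are run, and 4 patients are to be enrolled. Section 4.g declares success "If all 4 rs-fMRIs are completed and at least 3 of 4 Infinitome analyses are completed".

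**The concern.** Read literally, the criterion asks for tolerance of an fMRI lasting an hour, and the plan describes no such scan. Two consequences seem to follow.

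First, one screener might take the hour at face value and another might take it as the actual session. They could then admit different patients, and the literal reader could turn away someone able to finish the study scan. With 4 patients, one different decision changes a quarter of the sample.

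Second, the completion rate is measured only after patients expected not to tolerate the scan have been removed. Section 3 motivates the work by calling resting-state and diffusion imaging "both techniques that are time-consuming and impractical for clinical practice". If time in the scanner is part of that barrier, the patients most affected leave before anything is counted, and no tally of them is described. A 4/4 result would then look better than the sequence deserves across the mild-to-severe range that the inclusion criteria admit. Section 4.i wants the result "to justify standard use of the Infinitome program in clinical research", and Section 3 wants it to guide a subscription decision.

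**Working it through.** **Run time from the plan's own parameters.** 128 volumes × 2.8 s = 358.4 s = 5.97 min, against a stated figure of about 8 min. The stated figure is not reproduced; the gap is 8 − 5.97 ≈ 2 min. Set-up or dummy volumes could fill it, but none are listed. This is a separate matter inside Section 4.d and does not bear on the tolerance criterion.

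**The hour against the resting-state times.** 60/8 = 7.5 and 60/15 = 4. These ratios would show a contradiction only if the hour and the shorter figures measured the same thing. Section 6 limits 8–15 min to the resting-state portion and calls it additional, so they need not.

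**The hour as a whole session.** The time left for the clinical MRI and diffusion is 60 − 15 = 45 min to 60 − 8 = 52 min. The documents give no diffusion TR, so assume 6 to 12 s, and assume diffusion is not already inside the 8–15 min:

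- Shortest: 31 volumes × 6 s = 186 s = 3.1 min.
- Longest: 61 volumes × 12 s = 732 s = 12.2 min.
- All research imaging: 8 + 3.1 = 11.1 min to 15 + 12.2 = 27.2 min.
- Left for the clinical MRI: 60 − 27.2 = 32.8 min to 60 − 11.1 = 48.9 min.

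An hour is thus arithmetically possible for the session, though not for the resting-state run. The result depends on the assumed values. If clinical and diffusion imaging together take 20, 30 or 45 min (also assumed), the session is 28–35, 38–45 or 53–60 min, and only the last range reaches an hour.

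**What the screen could do to the 4/4 rule.** Let q be the share screened out, c1 the completion probability among those kept and c0 that among those removed. The unscreened rate is (1 − q)c1 + q·c0, and the chance of 4/4 is its fourth power. None of these inputs is in the documents. With c1 = 0.95, the chance with the screen is 0.95⁴ = 0.81. Without it:

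| q | c0 | Unscreened rate | Chance of 4/4 |
|---|---|---|---|
| 0.10 | 0 | 0.855 | 0.53 |
| 0.10 | 0.50 | 0.905 | 0.67 |
| 0.20 | 0 | 0.76 | 0.33 |
| 0.20 | 0.50 | 0.86 | 0.55 |
| any | 0.95 | 0.95 | 0.81 |

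The last row matters. If the criterion turns away people who would have finished just as often, the screen does not inflate the rate. The two halves of the concern therefore pull against each other: the more the hour over-excludes capable patients, the less it flatters completion.

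**The case for a change.** The best case for a change is that the criterion says fMRI, not session, and that nothing in the text tells a screener which is meant. The number of patients lost to expected intolerance is basic feasibility information and costs almost nothing to record, since staff already contact each interested patient. Without that number, a reader cannot tell which row of the table applies.

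Part of this stands. The hour is undefined, and the completion rate is conditional on a screen whose losses are not described as counted. Several things limit its force:

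- The study runs at one center, Section 4.c gives one role the task of identifying candidates, and the third exclusion criterion already leaves room for the investigator's judgement. Divergent readings across screeners are unlikely in 4 patients.
- Candidates must already have a clinical indication for MRI, so they are expected to undergo scanning anyway. How much further the second criterion filters is unknown.
- Section 3 speaks of clinical practicality in general and does not name patient intolerance as the cause. Section 2 asks whether the program can be used to evaluate network dysfunction; testing a time barrier is not an aim.
- Enrolled patients can still fail through motion, early stopping or technical faults, so the endpoint is not empty.
- The intended use is clinical research, where participants could likewise be screened for scan tolerance.
- The phone script mentioned in Section 4.c and the consent form were not available for this review and may state the total scan time.

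**Conclusion.** The concern does not call for a change. The text leaves the hour undefined, but the figures set against it cover only one part of a longer session, so no contradiction is shown. Staff who know the length of the booked scan can apply the criterion sensibly. Nothing here says which figure is right.

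Not scanning patients who cannot tolerate it is a normal trade-off. The denominator is already settled: 4 enrolled patients, eligible before the research sequences, with anyone who does not finish counted as a non-completer. A caveat that the result applies to eligible patients would be true of any eligibility criterion. A count of patients not enrolled for expected intolerance would be useful description, but it is optional. Followed as written, the endpoint, the 4/4 and 3/4 rule and the descriptive analysis are sound for the patients they cover.

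What remains is a point of interpretation: the completion rate may be optimistic about scan tolerance among all patients with Alzheimer's disease and an indicated MRI. Under the assumptions above, the chance of 4/4 without the screen ranges from 0.33 to 0.81, against 0.81 with it. That range reflects assumed inputs; the documents do not allow the actual effect to be computed. Section 4.i already concedes the small sample, and the plan rules out inferential statistics.

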## i. Consent

Potential research subjects will be informed that participation in this study is voluntary and that their decision to participate will not reflect upon their relationships with the Center for Memory and Aging, Regions Hospital, or HealthPartners. Subjects will be informed that they can withdraw from the study at any time and will be given a copy of the consent form.

With the electronic consent via REDCap the patient/caregiver providing consent will be able to review the consent form themselves and sign electronically with a stylus, touch screen, or cursor using a signature field in REDCap. After the individual has received the link and can view the consent form, the research staff member will go through the consent form with the individual as would be typical in person. If the patient/caregiver consents to participate, then they will sign via REDCap. After the signed consent form is received by study staff, the research staff member will sign another signature field and email a copy to the same email address to which the link was sent.

#### ii. Data sources

- Electronic medical records (EMR)
- Case Report Forms
- MRI Imaging
- Infinitome Program
- d. Intervention, treatments

There is no proposed treatment intervention.

**Imaging protocol described below**: Once settings are in place, apply these parameters for the BOLD imaging (what we call a T2\*EPI sequence)

## **Resting state fMRI**

- $3 \times 3 \times 3$ -mm voxels
- 128 volumes/run
- TE = 27 ms
- TR = 2.8 s
- field of view = 256 mm
- flip angle = 90°
- Run time about 8 min

# **Diffusion imaging protocol**

- one b0 baseline image
- B1000
- At least 30 and ideally 50-60 directions+ one baseline b0 scan
- FOV=25.6 cm
- slice thickness 2mm
- 0 mm gap between slices with no overlap
- full brain coverage
- isotropic voxels
- square 128x128 matrix
- 1 average/NEX
- axial foot to head slice prescription
- DTI done before contrast images

# e. Outcomes/endpoint and other variable definitions, and instruments used

Since this is a feasibility study, we are mainly evaluating the ability of the Infinitome program to detect connectome abnormalities in AD subjects.

- Rate of Completion of rs-fMRI % of subjects who completed the sequence of the fMRI protocol
- Rate of Completed Analysis % of subjects whose images were uploaded and analyzed by the Infinitome program
- Type of Abnormal Networks Identified All the abnormal networks as identified by the Infinotome program (categorical) such as default modal network..

Variable Name	Data Source	Purpose	Measurement Scale
	(patient survey, EMR, claims, registry)	(sample identification, description, grouping variable, study endpoint, predictor, covariate)	(binary, continuous)
Demographics (e.g., Age, Gender)	EMR	Description	Continuous, Binary
AD severity	EMR	Description	Categorical
MoCA (Montreal Cognitive Assessment)	EMR	Description	Continuous
fMRI – Program numbers and Post- processed Images	MRI and Infinitome program	Description/endpoint	Descriptive/Continuous

## g. Statistical analysis plan

Demographics and baseline characteristics of study participants will be summarized using descriptive statistics (mean and standard deviation, median, and proportions, as appropriate).

We will report the proportion of successfully completed rs-fMRIs and completed Infinitome analyses. If all 4 rs-fMRIs are completed and at least 3 of 4 Infinitome analyses are completed, we will consider this feasibility study a success.

We will also explore and report if any and which networks are identified as abnormal by the Infinitome program. The Infinitome output provides pairwise dysfunction between structures/areas within each network. We will report the number of patients who have dysfunction in the DMN, overall, as well as the number of pairwise structures within the DMN are dysfunctional. We may report on several other networks, if abnormality is shown.

h. No inferential statistics will be conducted for this study. We do not anticipate being able to definitively report areas that have dysfunction in persons with Alzheimer's; however, this preliminary data will be very important for future larger studies. Power analysis or statement of precision

If all 4 rs-fMRIs are completed and at least 3 of 4 Infinitome analyses are completed, we will consider this feasibility study a success. With a sample size of 4, we will be able to estimate a success rate of 75% to within a 95% confidence interval of +/- 21.7% assuming a true success rate of 75%.

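### Does the plan promise to detect network abnormalities in AD from 4 patients without controls, and is its DMN pair count unreadable without a denominator?

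*Combined protocol and SAP*

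**What the plan says.** All references are to the combined protocol and SAP.

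- **Aim (section 2).** The planned results are given as "rate of completion of rs-fMRI, rate of completed analysis of images using the program, and list the abnormal networks as identified by the program".
- **Sample (section 4.b).** "We plan to enroll 4 patients", all with a diagnosis of AD. No control group is described.
- **Reference (section 3).** The program compares a patient's network with a control cohort from the HCP. An attached vendor overview is cited; it was not available for this review.
- **Outcomes (section 4.e).** The opening sentence says "we are mainly evaluating the ability of the Infinitome program to detect connectome abnormalities in AD subjects". The listed outcomes are two completion rates and "All the abnormal networks as identified by the Infinotome program". The variable table adds the program's numbers and images.
- **Analysis (section 4.g).** The team will "report the number of patients who have dysfunction in the DMN, overall, as well as the number of pairwise structures within the DMN" that are dysfunctional. The number of DMN pairs evaluated is not given.
- **Inference and success (sections 4.g and 4.h).** There are no inferential statistics, and definitive statements about areas affected in AD are not expected. Success means 4 of 4 scans and at least 3 of 4 analyses completed.
- **Strengths and limitations (section 4.i).** A listed strength is "testing a novel program that leverages HCP data to determine dysfunctional connectomes in AD". On the other side, "Limitations of this study include the low number of subjects"; the absence of enrolled controls is not mentioned.

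**The concern.** Two things look wrong.

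First, the opening of section 4.e and the strength in section 4.i read as though the study will show whether the program detects disease-related abnormality. A study with no one free of AD cannot do that. It has no false-positive rate of its own, and the documents describe no matching of the HCP reference to this site's scanner or to patients aged 40 to 90.

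Second, a number of flagged DMN pairs has no scale unless the reader knows how many pairs were examined and how often the program flags pairs in its own controls.

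What would be at stake is how the results are read. Section 3 intends them as preliminary data for grant applications and as input to a decision on buying a subscription. Section 4.c says of the program's results: "This information will also be shared with the patient and family". If a bare count were taken as evidence of detection, both uses would rest on more than the design can support.

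**Working it through.** The plan gives no figure for the network results to reproduce. Its one precision statement, in section 4.h, concerns the success rate and does not bear on this point.

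**1. The patient count.** Inputs: n = 4 (section 4.b), or n = 3 if one analysis fails and the study still succeeds (section 4.g). When all n patients are flagged, the exact (Clopper-Pearson) 95% lower limit is 0.025^(1/n) and the upper limit is 1.

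- n = 4: 0.025^(1/4) = 0.398, so 40% to 100%.
- n = 3: 0.025^(1/3) = 0.292, so 29% to 100%.

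This width comes from the sample size, which section 4.i already names as a limitation. Listing the missing controls would not narrow it.

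**2. The pair count.** A network of k areas has k(k − 1)/2 pairs. The only area count in the documents is 379 for the whole brain (section 3), which gives 379 × 378/2 = 71,631 pairs. The DMN's share is not stated, so its size is assumed here.

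| Assumed DMN areas | Pairs | 10 flagged pairs as a share |
|---|---|---|
| 10 | 10 × 9/2 = 45 | 10/45 = 22% |
| 30 | 30 × 29/2 = 435 | 10/435 = 2.3% |

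**3. Chance flags.** Let a be the false-flag rate per pair and m the number of pairs, with pairs taken as independent. A person with no abnormality then has at least one flagged pair with probability 1 − (1 − a)^m. Both a and m are assumed.

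- m = 10 (5 areas), a = 0.27%: 1 − 0.9973^10 = 2.7%.
- m = 10, a = 5%: 1 − 0.95^10 = 40%.
- m = 780 (40 areas), a = 0.27%: 1 − 0.9973^780 = 88%.
- m = 780, a = 5%: practically 100%.

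The range is wide, so a bare count would indeed be hard to interpret.

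**4. Does the plan interpret it?** Set the statements side by side:

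- The section 2 aim and the outcome list in section 4.e agree: two completion rates and a list of networks.
- The success rule in section 4.g uses completion only. No number of flagged pairs or patients enters it.
- Section 4.g introduces the networks as something to explore and report. Section 4.h excludes inference and expects nothing definitive about AD.
- Section 3 explains that abnormality means a comparison with HCP controls.
- The section 4.e opening speaks of evaluating an ability, within a sentence that calls this a feasibility study. In section 4.i the phrase describes what the program is for.

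The two broad phrases are therefore not tied to any test, threshold or decision. Carrying out the plan as written yields completion proportions and a descriptive list, and neither depends on a control group.

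**The case for a change.** The best case for changing the plan is that the repair is cheap and the text is uneven. The main purpose in section 4.e matches neither the aim in section 2 nor the success rule in section 4.g. Section 4.i goes on to speak of justifying standard use of the program in clinical research, while omitting the lack of controls. Readers of a grant application, and families, may never see the caveat in section 4.h.

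Much of this is true. The opening of section 4.e is broader than the study, the absence of controls would be a fair limitation to list, and flagged pairs over evaluated pairs per patient is a better summary than a raw count. None of it shows that the plan would produce a wrong result. In section 3, detection describes what the future grants would do, not what this study will have shown. Families receive the program's output, which rewording sections 4.e and 4.i would not alter. Printing the vendor's control flag rate beside each patient could even invite the patient-versus-control reading it is meant to prevent, since that rate may not carry over to this scanner or these ages.

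**Conclusion.** No change is needed. The observations are accurate: 4 AD patients, 0 enrolled controls, and no stated number of DMN pairs. They affect neither the success criterion nor the decision to avoid inference, and the plan draws no conclusion about detection that would need correcting. What remains is loose wording in two sentences and a reporting detail that analysts can fill sensibly: give the DMN results per patient with a completed analysis, over the pairs evaluated, as differences from the HCP reference.

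This rests on two assumptions. One is that the report keeps the descriptive status set out in sections 4.g and 4.h. The other is that the program output, which section 4.g says is given pair by pair within each network, or the vendor overview allows the evaluated pairs to be counted. If the second fails, the pair count is less informative, but no planned conclusion changes. The 22% and 2.3% shares and the chance-flag probabilities depend on assumed network sizes and flag rates; they illustrate the point and are not estimates for this program.

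### The stated 95% confidence interval of ±21.7 points is one standard error, so the plan's only precision figure overstates precision about two-fold

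*Combined protocol and SAP*

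**What the plan says.** The sample size item under section 4.b states only "We plan to enroll 4 patients" and gives no rationale. Section 4.h, headed as the power analysis or statement of precision, says the study will be able to "estimate a success rate of 75% to within a 95% confidence interval of +/- 21.7% assuming a true success rate of 75"%. It names no interval method. This is the only precision figure in the document.

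Sections 4.g and 4.h both define success by counts: "If all 4 rs-fMRIs are completed and at least 3 of 4 Infinitome analyses are completed". The same part of the plan also says "No inferential statistics will be conducted for this study". In the extracted text this sentence follows the letter h and precedes the precision heading, so which subsection it belongs to is unclear.

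**The concern.** A 95% half-width of 21.7 points from 4 binary observations is implausibly small, since each patient moves the observed proportion by 25 points. The figure also matches a familiar intermediate quantity, the standard error at p = 0.75.

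Two further points follow from the same sentence:

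- It covers one rate, while the success rule uses two. For the scan rate the rule requires 4 of 4, where the normal-approximation formula gives an interval of zero width.
- It relies on a confidence interval, yet the plan excludes inferential statistics and nowhere says that an interval will be reported.

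The stake is how the result will be read. Section 3 says the findings will help decide whether to buy a subscription and will serve as preliminary data for grant applications. A reader who trusts the sentence would believe that 3 of 4 places the completion rate between about 53% and 97% with 95% confidence.

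**Working it through.** **Inputs.** n = 4 (sections 4.b and 4.h); assumed true rate p = 0.75, 95% confidence and stated half-width 21.7 points (all section 4.h). Sidedness is not stated; the ± sign implies a symmetric two-sided interval.

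**Step 1: reproduce the plan's figure.**

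SE = sqrt(p(1 − p)/n) = sqrt(0.75 × 0.25 / 4) = sqrt(0.046875) = 0.2165, which rounds to 21.7%.

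The stated value is one standard error to the printed precision. Under the normal approximation, ±1 SE is a 68% interval.

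**Step 2: the 95% half-width by the same formula.**

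1.96 × 0.2165 = 0.424, or 42.4 points. The interval is 75 ± 42.4, i.e. 32.6% to 117.4%. The upper limit is impossible, so putting 42.4 in place of 21.7 would not be an adequate repair.

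**Step 3: does any other usual method give 21.7?** Half-widths at n = 4 and 75% (for Wilson, Agresti-Coull and Clopper-Pearson, half the length of the interval for 3 of 4):

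| Method | Half-width (points) |
|---|---|
| Normal approximation, 95% two-sided | 42.4 |
| Normal approximation, 95% one-sided (same as 90% two-sided) | 35.6 |
| Normal approximation, 80% two-sided | 27.7 |
| Normal approximation with continuity correction | 54.9 |
| t with 3 degrees of freedom | 68.9 |
| Wilson | 32.7 |
| Agresti-Coull | 33.8 |
| Clopper-Pearson | 40.0 |

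None gives a symmetric 21.7. The upper arms alone of the Wilson (20.4), Agresti-Coull (21.6) and Jeffreys (22.2) intervals come close, but their lower arms are 44.9 to 46.6 points.

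**Step 4: a check that needs no interval method.** With 4 patients the observed rate can only be 0, 25, 50, 75 or 100%. If the true rate is 75%, the binomial probabilities of 2, 3 and 4 successes are 0.211, 0.422 and 0.316.

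- Within 21.7 points of 75% (53.3% to 96.7%), only 3 of 4 qualifies, because 2 of 4 and 4 of 4 are each 25 points away. The probability is 0.42, not 0.95.
- Within 42.4 points, all three outcomes qualify: 0.211 + 0.422 + 0.316 = 0.949.

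**Step 5: intervals suited to n = 4.**

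| Observed | Clopper-Pearson 95% | Wilson 95% |
|---|---|---|
| 3/4 | 19.4% to 99.4% | 30.1% to 95.4% |
| 4/4 | 39.8% to 100% | 51.0% to 100% |

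The exact 4/4 lower limit can be checked by hand: 0.025^(1/4) = 0.398. The exact 3/4 upper limit is 0.975^(1/4) = 0.994.

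**Step 6: size of the overstatement.** Relative to 21.7 points: 42.4/21.7 = 1.96 (normal approximation, using unrounded values), 40.0/21.7 = 1.84 (exact), 32.7/21.7 = 1.51 (Wilson).

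**Step 7: sample size that would give the stated precision.** n = 1.96² × 0.1875 / 0.217² = 15.3, rounded up to 16. This uses the normal approximation and is only a yardstick.

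**The case against.** The strongest reply is that the error has little consequence. Success is decided by counts, the plan does not say that 4 was derived from the precision figure, and correcting it changes no enrolment, procedure or decision. Section 4.i already names the small number of subjects as a limitation. Nothing shows that the planning half-width itself would enter the purchase decision or a grant application. All of this stands as a limit on impact. None of it makes the figure right, and no other text corrects it.

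Second, the two-fold factor depends on the method. That is true: it is closest for the normal approximation, which is the formula the plan evidently used, and smaller for Wilson. The overstatement is material under every method.

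Third, a planning statement about precision can sit beside a descriptive analysis. Many readers take inferential to mean hypothesis testing, the sentence may be aimed mainly at the network findings, and the plan does not say that intervals will be withheld. A precision statement also need not cover every proportion. These are fair points. The wording change and the interval for the second proportion are therefore clarifications that go with the main correction; they are not separate errors of the same weight.

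**Conclusion.** The concern holds. The figure given as a 95% half-width is a standard error. The correct normal-approximation value is 42.4 points, and an observed 3 of 4 is compatible with true rates from 19.4% to 99.4% (exact). The implied range of about 53% to 97% is far too narrow.

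The arithmetic rests only on the plan's own n = 4, p = 0.75 and 95%. That the multiplier was left out is an inference, but the match is exact to the printed digit and no standard alternative fits. The exact intervals treat the patients as independent with a common completion probability, as the plan's own calculation does.

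The error flatters the study and sits in the only precision statement it makes, so it should be corrected. It does not alter the enrolment target or the success rule.

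**What to change.** Keep n = 4. Replace the precision sentence in section 4.h with wording such as:

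> With 4 patients, an observed 3/4 (75%) has an exact (Clopper-Pearson) 95% confidence interval of 19.4% to 99.4%, and an observed 4/4 has one of 39.8% to 100%.

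This covers both thresholds in the success rule. In section 4.g, state that the scan completion and analysis completion proportions will each be reported with an exact 95% interval. Reword the exclusion of inferential statistics to say that no hypothesis tests will be done, so that it is consistent with reporting intervals.

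The cost is a few sentences of text and a less favourable stated precision. No extra patients, data or procedures are needed.
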